At each visit, patients will undergo a physical exam, vital signs, and an adverse event assessment. Peripheral blood will be drawn for a CBC with differential, serum chemistry with electrolytes, and liver function tests. On day +1 and day +8 of induction, prior to the administration of dexamethasone and palbociclib, patients will have blood drawn for pharmacokinetics. On day +1 and day +8 of induction, prior to the administration of dexamethasone, patients will also have blood drawn for pharmacodynamic studies. A bone marrow biopsy will performed to assess for response on day +28.

Maintenance Phase

Mandatory study visits will be conducted during the maintenance phase on the following days:

- Day +28

At this visit, patients will undergo a physical exam, vital signs, and an adverse event assessment. Peripheral blood will be drawn for a CBC with differential, serum chemistry with electrolytes, and liver function tests. A bone marrow biopsy will performed to assess for clinical response on day +28.

After the first cycle of maintenance, patients will be monitored with peripheral blood studies every other week. Bone marrow biopsy will only be performed if there is suspicion of relapsed disease.

See Appendix A for the Schedule of Events.

6.2.1 Dose Escalation Procedures

Dose Escalation Schedule										
	Dose*									
Dose Level	Palbociclib (mg)	Dexamethasone (mg)								
Level -1	75	20								
Level 1	100	20								
Level 2	125	20								
Level 3	150	20								
*Doses are stated as exact rather than as a percentag	t dose in units (e.g., mg ge.	g/m², mcg/kg, etc.)								

The dose escalation portion of this study will enroll within each cohort according to a "3+3 design", as explained in the following scheme. Palbociclib will be given as a 1 week lead in alone at the appropriate dose level. This will be followed by 4 weeks of Palbociclib in combination with dexamethasone (induction phase). Patients will receive dexamethasone 20mg daily from days 1-7, 16mg daily from days 8-14, 12mg daily from days 15-21, and 8g daily from days 22-28. Maintenance phase will consist of 1 week of Palbociclib with a dexamethasone 20mg daily followed by 3 weeks of Palbociclib alone. See Section 5.4 for Palbociclib dose modifications/dose levels.

Patients who experience a DLT during the evaluation period as defined below, will stop the study drugs and come off of the trial.

Patients who complete the first cycle of maintenance but require treatment to be held up to 4 weeks to achieve count recovery, will have Palbociclib resumed with a level -1 dose reduction.

The dose escalation portion of this study will follow a traditional 3+3 design, escalating to the next higher dose cohort if 3 patients are treated and no DLTs are observed in the first cycle of therapy. The following will be will be defined as a DLT:

Toxicity	DLT Criteria*								
Hematology	 Marrow aplasia (defined as <10% cellularity with <10% blasts for ≥ 6 weeks not attributable to disease) 								
	 Grade 4 neutropenia persisting ≥6 weeks from the start of a cycle that is not attributable to the underlying disease 								
Cardiac	Any ≥ Grade 3 toxicity								
Gastro-intestinal	Any ≥ Grade 3 toxicity except:								
	 Grade 3 nausea, vomiting**, or diarrhea** not requiring total parenteral nutrition (TPN) or tube-feeding 								
Hepato-biliary	An increase in AST or ALT >3 x ULN and concurrent increase in total bilirubin >2 x ULN (Hy's Law)								
	Any > Grade 3 toxicity except:								
	Any Grade 3 or 4 liver abnormalities (AST. ALT. or alkaline								
	phosphatase) that resolve to < grade 2 within 72 hours								
	 Grade 3 hyperbilirubinemia that resolves to < grade 2 within 72 hours 								
	 Grade 3 indirect hyperbilirubinemia that resolves to < grade 2 within 72 hours 								
Renal	Any ≥ Grade 3 toxicity								
Non-	≥ Grade 3, including electrolyte abnormalities, except as noted elsewhere in								
Hematologic	the table								
Exceptions to	Grade 3 alopecia								
DLI criteria	Grade 3 fatigue of < 5 days' duration								
	Grade 3 electrolyte abnormalities that last <72 hours								
	 Infection (including neutropenic fever), unless the investigator 								
	determines that the infection or neutropenic fever resulted from the degree or duration of myelosuppression in the absence of persistent								
	ieureillia								

* CTCAE version 5.0 should be used for grading.

** Optimal therapy for vomiting and diarrhea should be based on institutional guidelines with consideration of the prohibited medications listed in these protocol guidelines.

The DLT evaluation period is defined as 35 days (one week lead-in plus Cycle 1). In order to be considered evaluable, the patient needs to take 80% of the doses in the one week lead-in and Cycle 1 (1 cycle=28 days). The 80% completion can be non-consecutive days of dosing with study drug within the one week lead-in and Cycle 1. Any DLT will be followed until resolution.

If one DLT is recorded, then three additional patients will be enrolled into the present cohort. If no further DLTs occur (1 out of 6 DLTs) then the next patient will be enrolled in the next higher cohort. If 2 out of 6 patients have an observed DLT in any given cohort, 3 additional patients will be treated at one dose level lower, and if no additional DLTs are observed, this will be the maximum tolerated dose. If no DLTs are observed in all three cohorts then the expansion phase dose will be cohort 3 for the expansion phase. Toxicities will be graded according to the National Cancer Institute, Common Toxicity Criteria for Adverse Events version 4.0 (NCI CTCAE v5.0). If multiple toxicities are seen, the presence of DLT will be based on the most severe toxicity experience.

Once three patients have enrolled onto the dose cohort and the DLT evaluation period or the third patient has passed, a meeting will be held with the PI and the TJU Medical Monitor to review the safety information. If it is determined safe to open the next dose cohort, a formal letter from the Medical Monitor will be issued. Please see Appendix D for more information.

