1.4.1 Potential Risks

Patients will be informed of all anticipated and possible unanticipated adverse effects of drug treatments. Anticipated treatment-related adverse events include myelosuppression, nausea, vomiting, fatigue, diarrhea, anorexia, neutropenic fever, infection, pulmonary embolism, hyperglycemia, insomnia, adrenal suppression, myopathy, and psychiatric disturbances. Treatment-related mortality can occur from intensive anti-leukemic therapy and is estimated at 5-10%. Alternative therapies, including standard chemotherapy, investigational agents, and supportive care-only, will be discussed with potential patients prior to informed consent.

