11.2 Analysis Plans

This aim will consist of a Phase I trial of palbociclib to determine the maximum tolerated dose (MTD) of palbociclib when given in combination with dexamethasone. A standard 3+3 dose escalation design will be employed: three dose levels of palbociclib will be explored (100mg, 125mg, 150mg). Patients will be treated in cohorts of size three to six and the dosage will be escalated if the clinical toxicity is acceptable.

Patients who experience a DLT during the evaluation period as defined in section 6.2.1 will stop the study drugs and come off of the trial.

Patients who complete the first cycle of maintenance but require treatment to be held up to 4 weeks to achieve count recovery, will have palbociclib resumed with a level -1 dose reduction. A dose-limiting toxicity (DLT) is defined in the table below:

Toxicity	DLT Criteria*								
Hematology	 Marrow aplasia (defined as <10% cellularity with <10% blasts for ≥ 6 weeks not attributable to disease) 								
	• Grade 4 neutropenia persisting ≥6 weeks from the start of a cycle that								
	is not attributable to the underlying disease								
Cardiac	Any ≥ Grade 3 toxicity								
Gastro-intestinal	Any ≥ Grade 3 toxicity except:								
	 Grade 3 nausea, vomiting**, or diarrhea** not requiring total parenteral nutrition (TPN) or tube-feeding 								
Hepato-biliary	An increase in AST or ALT >3 x ULN and concurrent increase in total								
	bilirubin >2 x ULN (Hy's Law)								
	Any \geq Grade 3 toxicity except:								
	Any Grade 3 or 4 liver abnormalities (AST, ALT, or alkaline								
	phosphatase) that resolve to < grade 2 within 72 hours								
	 Grade 3 hyperbilirubinemia that resolves to < grade 2 within 72 hours One de 2 in dimensional that resolves to < grade 2 within 72 hours 								
	 Grade 3 indirect hyperbilirubinemia that resolves to < grade 2 within 72 hours 								
	nours								
Renal	Any ≥ Grade 3 toxicity								
Non-	≥ Grade 3, except as noted elsewhere in the table								
Hematologic									
Exceptions to	Grade 3 alopecia								
DLT criteria	 Grade 3 fatigue of < 5 days' duration 								
	 Grade 3 electrolyte abnormalities that last <72 hours 								
	 Infection, unless the investigator determines that the infection resulted 								
	from the degree or duration of myelosuppression in the absence of persistent leukemia								

* CTCAE version 5.0 should be used for grading.

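### The infection exception to the DLT criteria has no grade limit, so by default a treatment-related infectious death before the Day +28 marrow is left out of the escalation count

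*Combined protocol and SAP*

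**What the plan says.** The exceptions list in the Section 6.2.1 DLT table limits alopecia to Grade 3 and gives the next two entries as "Grade 3 fatigue of < 5 days' duration" and "Grade 3 electrolyte abnormalities that last <72 hours". The infection entry opens "Infection (including neutropenic fever), unless the investigator" and states no grade. An infection returns as a DLT only if the investigator "determines that the infection or neutropenic fever resulted from the degree or duration of myelosuppression in the absence of persistent" leukemia. The Section 11.2 table repeats the exception, again without a grade, as "Infection, unless the investigator determines that the infection resulted" and so on; it does not mention neutropenic fever.

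The general non-hematologic row makes Grade 3 or higher a DLT but gives way to entries elsewhere in the table. No row makes death a DLT.

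On timing, the DLT window is the one-week lead-in plus Cycle 1, 35 days in all (6.2.1). Section 6.2 says for induction: "A bone marrow biopsy will performed to assess for response on day +28". Appendix A allows ±2 days. Section 6.1 plans no earlier post-baseline marrow.

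On evaluability, a patient must take 80% of doses over the lead-in and Cycle 1, and a non-evaluable patient must be replaced (6.2.1, 11.3.1).

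On risk, Section 1.4.1 lists neutropenic fever and infection as anticipated treatment-related events and adds: "Treatment-related mortality can occur from intensive anti-leukemic therapy and is estimated at 5-10" percent.

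**The concern.** The exception reaches Grades 4 and 5 because nothing stops it. The clause that brings an infection back needs two findings: that myelosuppression caused it, and that leukemia does not persist. All patients enter with relapsed or refractory B-cell ALL (4.1.1), so leukemia is the starting state, and the planned test of whether it has gone comes at the end of the window. The plan does not say how to judge leukemia status before then.

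When a patient dies of a treatment-related infection during induction, the default reading is therefore that no DLT occurred. The evaluability rule can then remove that patient from the cohort. DLT and MTD are the primary endpoint (2.2.1). A plan followed to the letter could name an MTD whose DLT count omits fatal toxicity of the regimen.

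**Working it through.** **1. The plan's own figure.** Table 1.1 (11.2) follows from escalating on 0 of 3 or 1 of 6 DLTs:

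P(escalate) = (1−p)³ + 3p(1−p)² × (1−p)³ = (1−p)³ + 3p(1−p)⁵

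- p = 0.10: 0.729 + 0.177 = 0.906 (table 0.91)
- p = 0.20: 0.512 + 0.197 = 0.709 (table 0.71)
- p = 0.30: 0.343 + 0.151 = 0.494 (table 0.49)

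All nine entries reproduce. The arithmetic is sound, but p covers only events that the definition counts.

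**2. When leukemia status is planned to be known.** The window runs from Day −7 to Day +28: 7 + 28 = 35 days. The marrow falls on day 35, or with the −2 day allowance on Day +26, which is day 33. An infectious death before about Day +26 has no planned on-treatment marrow behind the leukemia condition.

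**3. When a patient becomes evaluable.** Counting daily palbociclib doses, 0.80 × 35 = 28. Seven are lead-in doses, so 28 is first reached on Day +21 (28 − 7 = 21) if none is missed. A patient who dies earlier without a DLT is non-evaluable and replaced. A patient who dies later, before the marrow, can stay in the count as a non-DLT.

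**4. Effect on escalation (assumed rates).** Take a true rate of 30%, part of it exempt infection.

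| Exempt infections | Rate the rule sees | P(escalate) |
|---|---|---|
| none | 0.30 | 0.49 |
| 10 points, counted as non-DLT | 0.20 | 0.71 |
| 20 points, counted as non-DLT | 0.10 | 0.91 |
| 20 points, patients replaced | 0.10 / 0.80 = 0.125 | 0.670 + 0.192 = 0.86 |

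For a wider range, let o be the rate of other DLTs and i the rate of severe treatment-related infection, assumed independent. The true rate is 1 − (1−o)(1−i).

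| o | Infections exempt | Counted, i = 5% | i = 10% | i = 20% | i = 30% |
|---|---|---|---|---|---|
| 5% | 0.973 | 0.910 | 0.824 | 0.622 | 0.425 |
| 10% | 0.906 | 0.824 | 0.730 | 0.536 | 0.360 |
| 20% | 0.709 | 0.622 | 0.536 | 0.378 | 0.248 |

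The table compares two extremes: all such infections exempt and kept as non-DLTs, or all counted. If the investigator called half of them DLTs, the result lies between (o = 10%, i = 20%: 0.730).

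**5. How often a treatment-related death might arise.** At the 5–10% in Section 1.4.1, the chance of at least one is 1 − 0.95³ = 14% to 1 − 0.90³ = 27% in three patients, and 1 − 0.95⁶ = 26% to 1 − 0.90⁶ = 47% in six. That figure covers all causes and is stated for intensive therapy in general, so it gives context and is not an infection rate for this regimen.

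**The case against.** The clause asks for the investigator's determination and does not require a marrow. Appendix A schedules CBC with differential on Days +1, +4, +8, +12, +14 and +21, and the investigator may use those results. Setting disease-driven events aside is also a visible choice: both hematologic DLT rows carry a similar limit, and relapsed leukemia can itself cause neutropenia and infection. All of this stands. It rules out the reading that an early infection can never be a DLT. The documents leave it open, with exemption as the default and no criterion for departing from it.

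A reader might also infer that three early infectious deaths would score 0 of 3 and send the dose up. The documents do not support that. Deaths before 28 doses lead to replacement. The PI and Medical Monitor review each cohort before the next opens (6.2.1), deaths go to the DSMC within 24 hours (8.4.2), Grade 5 events go to the IRB within one working day (8.4.1.3), and the study can be stopped for unacceptable risk (4.5). These are real safeguards. They do not change the DLT count or the MTD definition.

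Other organ rows (cardiac, renal, hepato-biliary) could capture organ failure in a septic patient. However, the 6.2.1 sentence that bases DLT status on the most severe toxicity leaves it unclear what happens when that toxicity is an exempt Grade 5 infection.

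Infection due to dexamethasone alone also stays exempt. That argument is weaker: the starting dexamethasone dose is the same at every level, so such infections do little to separate palbociclib doses, and they still appear in the safety analysis.

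**Conclusion.** The concern holds in this form: under both tables a treatment-related infectious death before the Day +28 marrow is by default not a DLT, and if fewer than 28 of 35 doses were taken the patient also leaves the escalation count. This is a rule that can give a wrong result for the primary endpoint, so it should be corrected and not merely clarified.

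That conclusion rests on the text alone. Its size rests on assumptions. Values of 0.71, 0.86 or 0.91 in place of 0.49 need a 30% true rate, the stated split, and an investigator who does not invoke the clause for those events. A reader might take 0.91 as the expected escalation probability, but no infection rate in the documents supports it. The figures also size the exemption as a whole. For fatal related infections only, the 5% and 10% columns are closer in kind (with other DLTs at 10%, 0.906 against 0.824 or 0.730), and those rates are assumed too.

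**What to change.** For the escalation count, state in both DLT tables that a Grade 5 infection at least possibly related to study treatment on the Section 8.3.1 scale is not covered by the exception. State in Section 11.3.1 that such a patient is counted and not replaced. Reconcile the two infection entries, since only Section 6.2.1 mentions neutropenic fever.

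The sponsor should also state how Grade 3–4 infections are classified and how leukemia status is judged before the Day +28 marrow. No rule is proposed for these, because a DLT also ends the patient's treatment; using relatedness at every grade would change who stops and could bring in many disease-driven infections. The Grade 5 change alters no patient's treatment.

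The cost is wording in two tables and one section, since relatedness is already recorded for every adverse event. The downside is that slightly more events count as DLTs, including some deaths that may be partly disease-driven, so escalation becomes somewhat more conservative.

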8.4.1.3 Serious Adverse Events

SAEs will be reported to the IRB on OHR-10 forms via the electronic reporting system (eSAEy) according to the required time frames described below.

Grade 3-4 AEs that are unexpected and deemed to be at least possibly related to the study will be reported to the IRB within 2 working days of knowledge of the event.

Grade 3-4 AEs that are deemed unrelated to the study will be reported to the IRB within 5 working days.

Grade 5 AEs will be reported to the IRB within one working day of knowledge of the event.

All SAEs will be submitted to the IRB at continuing review, including those that were reported previously.

8.4.2 **Reporting to SKCC DSMC**

All AEs and SAEs, safety and toxicity data, and any corrective actions will be submitted to the DSMC per the frequency described in the SKCC DSMP. The report to the SKCC DSMC will also include any unanticipated problems that in the opinion of the PI should be reported to the DSMC.

All non-hematologic adverse events will be reported to the DSMC.

The only hematologic events which will be considered a DLT/AE/SAE for this study are (i) marrow aplasia (defined as <10% cellularity with <10% blasts for \geq 6 weeks not attributable to disease) (ii) grade 4 neutropenia persisting \geq 6 weeks from the start of a cycle that is not attributable to the underlying disease and this will be reported.

All hematologic grade 5 SAEs will be reported to the DSMC regardless of causality.

For expedited reporting requirements, see table below:

DSMC AE/SAE Reporting Requirements

	Grade 1	Gra	de 2		Gı	ade 3		Grades 4 and 5
	Unexpected and Expected	Unexpected	Expected	Unex With Hospitalization	Unexpected Expected With Iospitalization Without Hospitalization With Hospitalization		Without Hospitalization	Unexpected and Expected
Unrelated Unlikely	Reviewed at Quarterly DSMC Meeting and	Reviewed at Quarterly DSMC Meeting and	Reviewed at Quarterly DSMC Meeting and	5 Working Days	Reviewed at Quarterly DSMC Meeting and IRB Annual	5 Working Days	Reviewed at Quarterly DSMC Meeting and IRB Annual	Phase I - 48 Hours (Death: 24 Hours)
	IRB IRB IRB Annual Annual Review Review Review			Review		Review	Phase II - 5 working days	
Possib le Prob ab ly	Reviewed at Quarterly DSMC Meeting	Reviewed at Quarterly DSMC Meeting	Reviewed at Quarterly DSMC Meeting	48 Hours (Death: 24	Phase I - 48 Hours	48 Hours (Death: 24	Reviewed at Quarterly DSMC	Phase I and Phase II - 48 Hours

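### Both hematologic DLTs need at least six weeks but the DLT window closes at Day +28, so neither can be met inside it, and no visible rule says whether a later-confirmed one counts

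*Combined protocol and SAP*

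**What the plan says.** Section 3 runs the palbociclib lead-in from Day -7 to Day -1, followed by a 28-day induction cycle. Section 6.2.1 states: "The DLT evaluation period is defined as 35 days (one week lead-in plus Cycle 1".

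The DLT tables in Sections 6.2.1 and 11.2 list two hematologic events:

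- "Grade 4 neutropenia persisting ≥6 weeks from the start of a cycle that is not attributable to the underlying disease"
- "Marrow aplasia (defined as <10% cellularity with <10% blasts for ≥ 6 weeks not attributable to disease"

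Section 8.4.2 adds: "The only hematologic events which will be considered a DLT/AE/SAE for this study are" these two.

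For escalation, Section 6.2.1 requires that "no DLTs are observed in the first cycle of therapy". The timing of the review is: "Once three patients have enrolled onto the dose cohort and the DLT evaluation period or the third patient has passed, a meeting will be held".

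Section 11.2 mentions the window only for stopping treatment: "Patients who experience a DLT during the evaluation period as defined in section 6.2.1" come off study drug. Its escalation rules (1) to (4) and both of its MTD statements give no time limit. Under Sections 6.2.1 and 11.3.1, a patient who took 80% of doses is evaluable.

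No visible text says whether a hematologic DLT confirmed after Day +28 counts toward the cohort total or the MTD. Appendix D, on dose-escalation approval, is listed but its text is not available here.

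**The concern.** DLT and MTD are the primary endpoint (Section 2.2.1). Section 1.2 reports that marrow suppression was the main dose-limiting toxicity of palbociclib in solid tumors, with an MTD of 125 mg; this trial goes to 150 mg. The two criteria meant to catch prolonged marrow toxicity take longer to satisfy than the period in which DLTs are assessed.

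A patient with grade 4 neutropenia or an aplastic marrow at Day +28 who took 80% of doses is evaluable and, at that point, has no DLT. If the six-week mark is passed later, the two sections point different ways. Suppose six patients are treated at 150 mg, one has a non-hematologic DLT inside the window, and another has neutropenia confirmed at Day +42. Not counting the second event gives 1/6, and 150 mg is the MTD. Counting it gives 2/6, and rule (3) of Section 11.2 says the MTD has been exceeded.

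**Working it through.** **1. Dates** (Sections 3 and 6.2.1)

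- Window: 7 + 28 = 35 days, from Day -7 to Day +28.
- Criterion: 6 weeks = 42 days.
- Neutropenia counted from Cycle 1 Day 1 qualifies at about Day +42, 14 days after the window closes. Counted from the first palbociclib dose, it qualifies at Day +35, still 7 days late.
- Aplasia has no stated start date. Counted from the first dose, it cannot qualify before Day +35. Dated from the first scheduled on-treatment marrow, it qualifies at Day +28 + 42 = Day +70.

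Neither criterion fits the window on any of these clocks.

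**2. The plan's own figures**

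Table 1.1 follows from P(escalate) = q³ + 3pq⁵, where p is the true DLT rate and q = 1 − p. For p = 10% to 90% this gives 0.906, 0.709, 0.494, 0.309, 0.172, 0.082, 0.032, 0.009 and 0.001, matching all nine entries. The formula assumes that every DLT is known when the decision is made.

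**3. Effect on escalation**

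The documents give no DLT rates, so these are assumptions: non-hematologic rate a = 0.10; independent hematologic rate h = 0.02, 0.05, 0.10 or 0.30; p = 1 − (1 − a)(1 − h).

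- *All DLTs known at review:* q³ + 3pq⁵.
- *Late events count, but only the third patient of each three is missed at review:* q²(1 − a) + [2pq² + q²a] × q²(1 − a). The bracket is exactly one DLT among the first three; patient 3's late status is known by the second review.
- *Late events never count:* the formula in step 2 with p = 0.10, i.e. 0.729 + 0.177 = 0.906.

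| h | p | All known | Third patient missed | Difference | Never count |
|---|---|---|---|---|---|
| 2% | 0.118 | 0.875 | 0.883 | 0.008 | 0.906 |
| 5% | 0.145 | 0.824 | 0.845 | 0.021 | 0.906 |
| 10% | 0.190 | 0.730 | 0.776 | 0.046 | 0.906 |
| 30% | 0.370 | 0.360 | 0.476 | 0.116 | 0.906 |

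Worked row, h = 5%: q = 0.855 and q² = 0.7310, so q²(1 − a) = 0.6579. The bracket is 0.2120 + 0.0731 = 0.2851. Then 0.6579 + 0.2851 × 0.6579 = 0.845.

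**4. How far along the earlier patients are**

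Accrual is 42 months (Section 11.3.2) for an anticipated 12 to 18 patients (Section 11.3). 42 × 30.4375 = 1278 days, so the average gap is 1278/18 = 71 to 1278/12 = 107 days. The earliest meeting is at the third patient's Day +28. A patient who started at least 14 days before the third has reached Day +42 by then. With exponential gaps of mean G (an assumption):

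- Patient 2: exp(−14/G) = 0.82 to 0.88.
- Patient 1: exp(−14/G)(1 + 14/G) = 0.98 to 0.99.

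**The case against.** **Confirmation at review.** A reader might infer that no hematologic DLT can ever be known at a cohort review. The documents do not support that. The end of the third patient's window is the earliest date for the meeting, not a deadline, and step 4 shows that the first two patients will usually have passed Day +42. The timing problem is confined to the last-enrolled patient and any enrolled close to that one. An earlier patient's event would still lie outside the defined window, so whether it counts is unstated for everyone.

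**Intent.** Section 1.2 treats marrow suppression as expected in leukemia and possibly a marker of efficacy, and the first-cycle wording points toward not counting later events for escalation. That is a fair reading. It leaves two listed DLTs with no role in escalation, and it does not settle the MTD tally in Section 11.2.

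**Safeguards.** Infection or neutropenic fever can be a DLT within the window if the investigator "determines that the infection or neutropenic fever resulted from the degree or duration of myelosuppression in the absence of persistent" leukemia. The Day +28 blood count and marrow are available at review, and the Medical Monitor must agree before the next cohort opens. DLTs are followed to resolution and late toxicity for one year, so the data would exist. These limit the risk to patients, but none is a counting rule.

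**Size.** A reader might take the contrast between 0.91 and 0.36 as the expected effect. It sets an upper bound against full capture at a 30% hematologic rate that nothing in the documents supports.

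**Reporting.** A reader might also conclude from Section 8.4.2 that shorter grade 4 neutropenia is not an adverse event here. Section 8.1.2 includes abnormal laboratory findings among adverse events, so the documents conflict and that conclusion is not safe.

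**Conclusion.** The rule is wrong as written. A 35-day window cannot contain a 42-day criterion, and that finding needs no assumption. Sections 6.2.1 and 11.2 then allow the same late-confirmed event to be counted or ignored, which can change the reported MTD. No visible text resolves this, with the reservation that Appendix D could not be read.

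The numerical effect depends on assumed rates. If late events count and only the third patient's is missed at review, the probability of escalating is too high by about 0.01 at a 2% hematologic DLT rate, 0.02 at 5%, 0.05 at 10% and 0.12 at 30%. If late events never count, it stays at 0.91 whatever the hematologic rate. That is the upper bound, because it gives no credit to the Medical Monitor's judgment or to the infection route. Nothing here shows that the trial would select an unsafe dose.

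**What to change.** Add to Sections 6.2.1 and 11.2:

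> (a) A hematologic DLT that begins in the lead-in or Cycle 1 and is confirmed after Day +28 counts toward that cohort's DLT total and the MTD.
>
> (b) If at Day +28 a patient has grade 4 neutropenia, or a marrow with <10% cellularity and <10% blasts, not attributable to disease, DLT status is pending. The next cohort does not open until the finding resolves or meets the existing 6-week criterion (neutropenia: Day +42, six weeks from Cycle 1 Day 1, on blood counts).

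The six-week aplasia definition and the repeat marrow at count recovery in Section 3 stay as they are.

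The cost is wording, blood counts during the hold (Appendix A lists no hold visit), and a delay only in cohorts with a pending patient. The delay is about 2 weeks for neutropenia (Day +28 to Day +42) and up to about 6 weeks for aplasia (Day +28 to Day +70). Both are shorter than the average 71 to 107 days between patients.

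Two practical points remain. The hold in Section 3 ends at Day +56, so following aplasia to Day +70 relies on the existing provision to follow events until they resolve. A neutropenic patient with a cellular marrow may already be on maintenance by Day +42, so that count may also reflect further palbociclib.
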